- □ intake of long-acting NSAIDs or application of topical medication since the injury (RICE allowed)
- □ participation in a clinical study within 30 days before inclusion in the study or concomitantly
- □ drug or alcohol abuse in the opinion of the investigator
- \Box pregnant and lactating women
- □ women of child-bearing potential without medically accepted contraception
- □ known hypersensitivity to Esflurbiprofen or one of the excipients of the patch
- □ patients with any ongoing condition that may interfere with the absorption, distribution, metabolism, or excretion of Esflurbiprofen
- history of previous significant injury to the same extremity within 6 months
- □ patients with a disease affecting the same limb, such as synovitis, rheumatoid arthritis, arthrosis, etc.
- □ patients having an ongoing painful condition associated with sports-related injury/contusion
- □ patients suffering from symptoms of an infectious disease including swelling of any joint of the affected upper or lower limbs
- □ patients who had surgery of the affected upper or lower limb within one year of study entry
- □ patients with significant diseases (defined as a disease which, in the opinion of the investigator, may either put the patient at risk because of participation in the study or a disease which may influence the results of the study or the patient's ability to participate in the study; includes patients with a history of gastrointestinal bleeding, significant cardiovascular, liver or renal disease).
- \Box patients with a blood coagulation disorder
- □ patients who use any impermissible medication (see below)

Concomitant Treatment 1. Rescue medication

In case of unbearable pain, patients are allowed to take paracetamol tablets (2 x 500 mg). Patients needing more than 6

Confidential Final Version 3.0

tablets (3 g) per day or another drug from the list of impermissible medication will be withdrawn from the study as non-responders. Application of standard care by rest, ice, compression (non-occlusive bandage), or elevation (RICE) can be considered at the

discretion of the Investigator. Also allowed are:

the use of crutches,

elastic, temporary bandages, that could be easily removed to assess the primary variable.

Physiotherapeutic measures (i.e. isomeric exercises to train the muscles) if they don't interact with the injured area

2. Impermissible medication

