6.5.9 Study drug discontinuation and premature patient withdrawal

The study drug must be discontinued and the patient withdrawn from the study if the Investigator determines that continuing it would result in a significant safety risk for that patient. The following circumstances require study drug discontinuation:

- □ Withdrawal of informed consent
- □ Pregnancy
- □ Emergence of any clinically relevant serious adverse events
- Any other protocol deviation that results in a significant risk to the patient's safety

In addition to these requirements for study drug discontinuation, the Investigator should discontinue study drug for a given patient if, on balance, he/she thinks that continuation would be detrimental to the patient's well-being.

Patients may voluntarily withdraw from the study for any reason at any time. They may be considered withdrawn if they state an intention to withdraw, or fail to return for visits, or become lost to follow up for any other reason. If premature withdrawal occurs for any reason, the Investigator must determine the primary reason for a patient's premature withdrawal from the study and this information must be recorded on the Study Completion CRF.

Patients who are prematurely withdrawn from the study will not be replaced.

If a patient is discontinued or decides to withdraw from the study, all evaluations scheduled for the final visit will be performed within one week of study drug discontinuation. Every effort must be made to collect all the required data at the time of patient discontinuation. The Investigator or designee must complete the Study Drug Discontinuation, giving the date and primary reason for stopping the study drug.

For patients who are lost to follow-up (i.e. those patients whose status is unclear because they fail to appear for study visits without stating an intention to withdraw), the Investigator or designee should show "due diligence" by documenting in the source documents the steps taken to contact the patient, e.g. dates of telephone calls, registered letters, etc., in order to establish the reason for discontinuation and to check presence of any AEs.

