5.1.2 Secondary efficacy variables

- POM at injured site in mm measured using a 100 mm VAS at 12, 24, 48, 72, 96 and 168 hours after commencement of study treatment and will additionally presented by subgroups (table and Figure).
- AUC over time during first 12, 24, 48, 72, 96 and 168 hours for POM measured using a VAS; ordinate = POM score in mm, abscissa = time after treatment
- Pain-at-rest (PAR) at injured site in mm measured using a 100 mm VAS at 12, 24, 48 72, 96 and 168 hours.
- Reduction in VAS for POM from baseline:
 - Time to meaningful reduction (30%)
 - \circ Time to optimal reduction (50%)
 - Time to complete resolution of pain
- Responder rate 1 (defined as the proportion of patients achieving ≥50% reduction from baseline in the VAS score for POM at 72 hours)
- Responder rate 2 (defined as the proportion of patients able to resume training / normal physical activity by 168 hours)
- Clinical global assessment of efficacy as judged by investigator and patient at 48, 72 and 168 hours
- Overall dose of rescue medication needed (paracetamol).
- POM on VAS by indication at Visit 5.

Additional outcomes

- Adhesive power of patch (5-point scale)
- Mean adhesion by application site and/or net use.
- If there is significant use of rescue medication, a sensitivity analysis may be performed to assess impact on primary endpoint and responder rate.
- Outcomes will be compared for all use of rescue medication and separately for use to treat blunt trauma. Day 1 and the day of the final visit will count as full days for this purpose. Use of rescue medication on days after study medication has been discontinued will not be counted.
- POM on VAS difference at V4, V5, V6 compared to V1 (BL) (PID V4, PID V5, PID V6) PID V4, PID V5 and PID V6 will be compared between treatment groups using ANCOVA with terms in the model for treatment group, site [as fixed effects], and baseline POM assessment [as a covariate]. Least square mean for each treatment and the

CRMB	Trial Substance:	Esflurbiprofen Hydrogel Patch	Study No.: EudraCT No.:	TK-254R-0201 2020-005165-14
	Short Title:	Local symptomatic and short-term treatment of pain in acute strains, sprains or bruises of the extremities following blunt trauma		OKU SEIYAKU CO LTD.

corresponding difference between least square means with the p-value and 95 % confidence interval will be presented from the specified ANCOVA model.

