14.4.2 Secondary efficacy variables

- POM at injured site in mm measured using a 100 mm VAS at 12, 24, 48, 72, 96 and 168 hours after commencement of study treatment and will additionally presented by subgroup (table and Figure).
- AUC over time during first 12, 24, 48, 72, 96 and 168 hours for POM measured using a VAS; ordinate = POM score in mm, abscissa = time after treatment
- Pain-at-rest (PAR) at injured site in mm measured using a 100 mm VAS at 12, 24, 48 72, 96 and 168 hours.
- Reduction in VAS for POM from baseline:
- Time to meaningful reduction (30%)
- Time to optimal reduction (50%)
- Time to complete resolution of pain
- Responder rate 1 (defined as the proportion of patients achieving ≥50% reduction from baseline in the VAS score for POM at 72 hours)
- Responder rate 2 (defined as the proportion of patients able to resume training / normal physical activity by 168 hours)
- Clinical global assessment of efficacy as judged by investigator and patient at 48, 72 and 168 hours
- Overall dose of rescue medication needed (paracetamol).

Statistical test results for secondary variables will only be interpreted exploratorily.

Other important secondary efficacy outcomes are pain-on-movement on VAS at 12, 24, 48, 72, 96 and 168 hours after initiating treatment in the FAS population. These will be analyzed with an analysis-of-covariance (ANCOVA) model and center and subgroup as main effects. All other continuous efficacy outcomes will be analyzed based on the same model (excluding the baseline covariate when there is no appropriate baseline).

Differences between treatments on ordinal outcomes will be tested with Wilcoxon, stratified by center and subgroup.

Figures will show the time course of outcomes by treatment group for key quantitative outcomes. The primary outcome will also be summarized by center (if there is evidence of a treatment-by-center interaction), sex, age and race but without formal statistical comparisons of treatments.

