14.8 Missing data

- If assessments at any visit for Visits 2 (12 h) through Visit 6 (96 h) are missing, they will be imputed as the average of the preceding and the following assessments. Fractional values will be rounded down (including ordered categorical assessments). If assessment at Visit 7 is missing, the last observation will be carried forward.
- If a patient terminates prematurely,
 - all subsequent visits will be imputed by carrying the last non-missing observation forward.
 - for an adverse event suspected to be study-drug-related, then all subsequent visits will be imputed by carrying the baseline observation forward.
 - for lack of efficacy, all subsequent assessments will be imputed as the worst of all documented assessments.
 - for lack of efficacy or for an adverse event suspected to be study-drug-related and does not complete the global assessment of treatment satisfaction, it will be assigned the worst possible score.

CRMB	Trial Substance:	Esflurbiprofen Hydrogel Patch	Study No.: EudraCT No.:	TK-254R-0201 2020-005165-14
	Short Title:	Local symptomatic and short-term treatment of pain in acute strains, sprains or bruises of the extremities following blunt trauma	Sponsor: TEIKO	KU SEIYAKU CO LTD.

- If a patient discontinues for any other reason, missing global assessments at Visit
 7 will be imputed by LOCF from Visit 5 and missing assessments at Visit 5 will not be imputed.
- If a patient assesses efficacy at the site < 6 hours after using rescue medication, imputation will be discussed in the Blind Review Meeting, with consideration given to the frequency of this issue in the database and the elapsed time between rescue and assessment of efficacy.
- If a patient assesses spontaneous pain intensity and spontaneous pain relief at the time of rescue taken because of blunt trauma pain, any assessment conducted in the following 6 h will be replaced by the corresponding assessment done at the time of rescue.
- If a patient assesses spontaneous pain intensity and spontaneous pain relief at the time of rescue taken for reason other than blunt trauma pain, any assessment conducted in the following 6 h will be imputed as if the assessment were missed.
- If there are no assessments in the 12-24 h window, or the 24-48 h window,
 - if the patient has not prematurely terminated, a value from the last preceding assessment or assessment window will be carried forward.

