14.9 Censoring

- Time to meaningful relief will be censored (if appropriate) at the time of the final assessment of meaningful relief. If the patient discontinues for lack of efficacy before achieving meaningful relief, it will be censored at 24 h.
- Time to perceptible relief will be censored (if appropriate) at 24h or the time of final assessment of spontaneous pain relief (if earlier). If the patient discontinues for lack of efficacy before achieving perceptible relief it will be censored at 24 h.
- Time to resolution of blunt trauma will be censored (if appropriate) at the day of the final visit. If the patient discontinues for lack of efficacy, it will be censored at 7 days.
- Time to first use of rescue medication will be censored (if appropriate) at the last day for which diary records are available.

If a patient takes a disallowed analgesic medication and subsequently provides efficacy assessments, rules will be established on a case-by-case basis, taking into consideration whether the disallowed analgesic medication was taken to treat pain in the injured area and the likely duration of effect of the medication. The rules will be documented before the study is unblinded.

Additional data handling rules will be specified in the minutes of the BRM, if any, to cover issues not anticipated in the above stipulations.

CRMB	Trial Substance:	Esflurbiprofen Hydrogel Patch		-254R-0201 20-005165-14	
	Short Title:	Local symptomatic and short-term treatment of pain in acute strains, sprains or bruises of the extremities following blunt trauma	Sponsor: TEIKOKU SEIYAKU CO LTD.		

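### The synopsis labels patients withdrawn for excess rescue or a banned drug as non-responders, but no analysis rule says so, and default LOCF can make them responders at 72 h

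*Protocol*

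**What the plan says.** **Protocol Synopsis, Concomitant Treatment.** Patients needing more than 6 paracetamol "tablets (3 g) per day or another drug from the list of impermissible medication will be withdrawn from the study". The same sentence attaches an outcome label: "medication will be withdrawn from the study as non-responders".

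**Protocol 6.5.5, 6.5.6 and 6.5.9.** The first two give the daily maximum and the prohibited drugs but no consequence for the patient's outcome. Section 6.5.9 opens its list with "The following circumstances require study drug discontinuation", and neither excess rescue nor prohibited medication is on it.

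**SAP 5.1.2 and 14.4.2.** Responder rate 1 is the "proportion of patients achieving ≥50% reduction from baseline in the VAS score for POM at 72 hours". There is no override for these withdrawals.

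**SAP 14.8.** After early termination the default is that "all subsequent visits will be imputed by carrying the last non-missing observation forward". There are two exceptions for POM. A suspected drug-related adverse event takes the baseline value. The other reads: "for lack of efficacy, all subsequent assessments will be imputed as the worst of all documented assessments". Protocol 9.7.3 has the same structure, with a slightly different lack-of-efficacy rule (the worse of the final and baseline scores).

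**SAP 14.9.** For patients who take a disallowed analgesic and later give efficacy scores, "rules will be established on a case-by-case basis", to be documented before unblinding.

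**The concern.** The synopsis treats these patients as failures. The SAP lets their 72 h value depend on which withdrawal reason is recorded. If the reason is, for example, a protocol deviation or prohibited medication, LOCF applies, and the score carried forward may have been lowered by the very analgesic that led to withdrawal. For disallowed analgesics, the case-by-case clause leaves the same possibility open.

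Two results depend on this. Responder rate 1 can count as a success someone the protocol calls a non-responder. The same 72 h POM value also feeds the primary ANCOVA in the FAS, where these patients remain. If more placebo than active patients pass the rescue limit, the estimated effect shrinks.

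**Working it through.** **Step 1: which SAP rule applies.** Take a patient withdrawn under the synopsis rule before Visit 5, with assumed POM scores of 70 mm at baseline, 60 mm at 12 h and 30 mm at 24 h after paracetamol.

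| Recorded reason | SAP 14.8 rule | 72 h value | Reduction | Responder rate 1 |
|---|---|---|---|---|
| Lack of efficacy | worst documented | max(70, 60, 30) = 70 mm | (70 − 70)/70 = 0% | no |
| Suspected drug-related AE | baseline carried forward | 70 mm | 0% | no |
| Anything else | LOCF | 30 mm | (70 − 30)/70 = 57% | **yes** |

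The synopsis label is non-responder in every row. The first two rows agree with it whatever the scores, because neither value can be better than baseline. Only the third row conflicts. Protocol 6.5.9 asks for a primary reason and SAP 14.11 allows several, but neither ties this withdrawal to a category.

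**Step 2: whether other provisions close the gap.**
- The 6 h rescue-free period (Protocol 6.5.5) precedes Visit 5 only. Visits 2 to 4, the usual donors for LOCF, have none.
- The SAP 14.8 rule that replaces scores within 6 h of rescue for trauma pain uses ratings made at the time of rescue. The diary (Protocol 6.5.8) collects spontaneous pain then, not POM, so there is no POM score to substitute.
- Site scores taken less than 6 h after rescue are left to the Blind Review Meeting.
- The rescue sensitivity analysis is optional, and its trigger, significant use, is not defined.

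**Step 3: the plan's own figure.** For a 10 mm difference, SD 20 mm, two-sided 5% and 80% power, the exact two-sample t-test gives 63.8, so 64 per group, with 80.1% power at 64. The plan's figure is reproduced and is not in dispute.

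**Step 4: size on the primary effect.** The documents give no withdrawal rates, so these inputs are assumptions. Let p_P and p_A be the proportions on placebo and active withdrawn under the rule before Visit 5 and handled by LOCF. Let the gap be the worst score minus the LOCF score, here 70 − 30 = 40 mm as in the example.

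Shift = (p_P − p_A) × gap

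Power ≈ Φ(δ / (20 × √(2/90)) − 1.96), where 20 × √(2/90) = 2.98 mm. This uses n = 90 per group and takes 10 mm as the effect when these patients are handled as failures.

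| p_P − p_A | Shift | Remaining effect | Power |
|---|---|---|---|
| 0 | 0 mm | 10 mm | 92% |
| 0.02 | 0.02 × 40 = 0.8 mm | 9.2 mm | 87% |
| 0.05 (e.g. 8% v 3%) | 0.05 × 40 = 2.0 mm | 8.0 mm | 76% |

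**Step 5: size on responder rate 1.** With 100 per arm, each reclassified patient moves that arm's rate by 1 point. A 5-point imbalance therefore moves the difference by at most 5 points.

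**The case against.** The strongest reply is that withdrawing someone as a non-responder naturally means lack of efficacy. SAP 14.8 then assigns the worst documented score and the patient is a non-responder, so the plan needs only a clarification. This stands in part. Misclassification is possible, not automatic, and a reader who infers that the SAP always turns these patients into responders goes too far. It would also be wrong to infer that every reason other than lack of efficacy leads to LOCF, since suspected drug-related adverse events take the baseline value. But nothing in the SAP requires the lack-of-efficacy coding, and excess rescue or a banned drug could as easily be recorded as a deviation.

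A second reply is that safeguards exist. The per-protocol set excludes patients who took pain medication, and the case-by-case rules must weigh why the drug was taken and how long it acts, and must be fixed before unblinding. That rules out choice by arm. It does not settle the FAS analysis, which is primary.

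Third, the 2 mm figure sits at the high end. Rates of 8% and 3% in arms of 100 are 8 + 3 = 11 patients, over half of the 20 dropouts planned for (10% of 200). All would have to stop before 72 h, be coded outside both exceptions and carry forward a low score. This is fair. No document shows that excess rescue is commoner on placebo either. If it is, the cost is power and not a false-positive risk. Responder rate 1 is also secondary and exploratory.

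Fourth, a reader might infer that everyone meeting the synopsis rule should get the worst score. The documents do not support that. The impermissible list includes heparin and psychotropic agents, paracetamol is also allowed for headache or fever, and SAP 14.8 itself separates rescue for trauma pain from rescue for other reasons.

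**Conclusion.** The point holds as a conflict between the protocol's label and the SAP's rules. The synopsis classes these patients as non-responders, while the SAP as written can count them as responders and put an analgesic-lowered POM score into the primary ANCOVA. This happens only when the recorded reason is neither lack of efficacy nor a suspected drug-related adverse event, or when a case-by-case rule accepts the score.

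The size cannot be taken from the documents. It equals the excess proportion in one arm times the handling gap: 0.8 mm for 2 points and 2 mm for 5 points with an assumed 40 mm gap, or 8% and 20% of the 10 mm target. It is toward the null if the excess is on placebo, the other way if it is on active, and near zero if rates are equal. Neither figure is a forecast. The case for acting is that the rule is undefined and cheap to define.

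**What to change.** 1. Reconcile the Protocol Synopsis with Protocol 6.5.5, 6.5.9 and 9.7.3 and SAP 14.8 and 14.9, so that all say the same about these withdrawals and their outcome. No view is taken here on the rescue limit or the withdrawal rule itself.
2. In SAP 5.1.2 and 14.4.2, state that patients withdrawn under the synopsis rule because of injury pain are non-responders for responder rate 1, whatever VAS value is imputed.
3. In SAP 14.8, state that their POM after withdrawal is imputed under the existing lack-of-efficacy rule, regardless of the reason recorded.
4. Leave the SAP's separate handling in place for impermissible drugs or rescue taken for reasons other than injury pain. The case-by-case clause in SAP 14.9 can remain for those patients.

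The cost is SAP wording and one protocol reconciliation, before unblinding. The downside is small: some scores measured after disallowed analgesics are set aside.

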With an increasing number of people undertaking sports activities and with a parallel increase in the number of acute contusions, there is a need for an effective alternative treatment available with better tolerability. Topically applied Esflurbiprofen has been shown to have low systemic bioavailability. Based on those existing data the novel Esflurbiprofen 165 mg Hydrogel Patch which is the target treatment of this study is not expected to significantly exceed 10% of the systemic exposure achieved following standard oral dosing with Flurbiprofen 100 mg tablets (3 times a day). Accordingly, it is appropriate to test the efficacy and safety of the Esflurbiprofen Hydrogel Patch in the treatment of blunt injuries.

A parallel-group design is utilized as a within patient comparison based on repeated or simultaneous contusions is clearly inappropriate. Measurement of pain and disability over approx. 72 hours should be sufficient to prove efficacy based on previous experience [Predel 2004, Bonnekoh 1992, Hess 1996, Pabst 2001]. Dosing continues through resolution of the injury in order to adequately assess safety over the entire dosing interval.

POM measured by VAS at 12, 24, 48 and 72 hours after initiating treatment (clinic visit) are important secondary endpoints to demonstrate an early and continued of treatment effect.

The overall reduction of pain on movement after 72 hours is considered a good indicator to assess the postulated efficacy in the frame of this proof-of-concept study.

Patients should be treated as soon as possible after the injury because early treatment may reduce swelling, thereby increasing the likelihood of treatment success. Treatment will therefore be initiated no more than 6 hours after the blunt injuries event.

To minimize unnecessary risk to patients during study participation they will be screened at baseline to ensure absence of the various clinical disorders described in the exclusion criteria. This comprehensive process will include a baseline physical examination, vital signs, medical and drug history.

To avoid bias, double blinding and randomization are important features of this study.

3 Objectives

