7.3 Assessment of injury

The size of injury is measured by the Investigator. The size must be at least 25 cm² and at most 120 cm^2 on the basis of the largest perpendicular diameters. The localization should also be documented in detail in the patient CRF.

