5.3 Other variables

The following other variables are documented in this clinical trial:

- Demographics and other baseline characteristics (documented at Visit 1; age, sex, height, weight, race, ethnicity, localization of injury).
- Check of contraception (at Visit 1).
- Medical history (at Visit 1).
- Concomitant medication (every visit).

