6 SAMPLE SIZE

The calculation of 90 per treatment group is based on the following assumptions and considerations:

- Primary efficacy outcome is the change from baseline for POM at 72 hours after initiating treatment.
- Two-sided t-test situation with $\alpha = 5\%$.
- Assuming SD = 20 mm, the sample size provides approximately 80% power to detect a difference of 10 mm between two treatment groups if 64 patients per group are analysed.
- However, the sample size will be stipulated to n=90 per group in order to power also the two subgroup comparisons.
- Moreover, the sample size will be a total of 200 patients because a dropout-rate of approximately 10 % is taken into account.

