14.4 Efficacy

14.4.1 Primary efficacy variable

Change from baseline in pain-on-movement (POM) at injured site in mm measured using a 100 mm Visual Analogue Scale (VAS) to Visit 5 (72 hours after commencement of study treatment)

The analysis of the primary endpoint will be adjusted for baseline values. The baseline adjusted difference between active treatment and placebo at 72 hours should be > 10 mm. Magnitude of reduction in pain will be used to determine 'responder rate'.

For the primary variable an analysis-of-covariance (ANCOVA) with baseline as covariate and treatment, center and subgroup as factors will be carried out. A closed testing procedure controlling the multiple α -level of 5 % will be used in the analysis:

1) H₀: $\mu_E=\mu_P$ vs. H₁: $\mu_E\neq\mu_P$. In case of a significant result for this first hypothesis two further hypotheses regarding the subgroups "sprains/strains" and "contusions" will be then be also tested by means of the same baseline adjusted ANCOVA model to the 5 % level. In case of significance, the following subhypotheses are simultaneously tested at the 5 % level of significance.

2a) H₀: $\mu_E(\text{spr/str})=\mu_P(\text{spr/str})$ vs. H₁: $\mu_E(\text{spr/str})\neq\mu_P(\text{spr/str})$ in the subgroup "Sprains/strains",

2b) H₀: $\mu_E(con) = \mu_P(con)$ vs. H₁: $\mu_E(con) \neq \mu_P(con)$ in the subgroup "contusions".

CRMB	Trial Substance:	Esflurbiprofen Hydrogel Patch	Study No.: TK-254R-0201 EudraCT No.: 2020-005165-14
	Short Title:	Local symptomatic and short-term treatment of pain in acute strains, sprains or bruises of the extremities following blunt trauma	Sponsor: TEIKOKU SEIYAKU CO LTD.

The primary analysis population is the Full Analysis Set (FAS).

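### Injury size is measured at Visit 1, and delay to treatment is given as a reason for the entry limit, yet neither is in the primary ANCOVA or the SAP's baseline list: a cheap, modest gain left unused

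*Protocol*

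**What the plan says.** **Model.** SAP 14.4.1 specifies for the primary variable that an "analysis-of-covariance (ANCOVA) with baseline as covariate and treatment, center and subgroup as factors will be carried out". Protocol 9.7.2 and the synopsis name the same terms. Tests 2a (sprains/strains) and 2b (contusions) use the same baseline-adjusted model. Randomization is stratified by center and subgroup (protocol 4 and 6.3).

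**Injury size.** Protocol 7.3 states: "The size of injury is measured by the Investigator". The permitted range is 25 to 120 cm², which is also inclusion criterion 5, and the Visit 1 procedures in section 7 include the assessment.

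**Delay.** Protocol section 2 wants patients treated quickly "because early treatment may reduce swelling, thereby increasing the likelihood of treatment success" and derives the 6-hour limit from this. Sections 2 and 4 apply the limit to first treatment, while inclusion criterion 3 applies it to enrollment. No section names hours since injury as a variable to be recorded, summarised or analysed.

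**Baseline reporting.** SAP 5.3 lists the demographic and baseline characteristics as "age, sex, height, weight, race, ethnicity, localization of injury". Localization is there; size and delay are not. Protocol 7.2 names neither. Protocol 9.5 and SAP 14.3 promise summaries of other baseline characteristics by arm and subgroup but do not add to the list.

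**The concern.** Two baseline quantities matter enough to be entry criteria, and for one of them the protocol gives a reason why it could affect the result. Eligible sizes span a 4.8-fold range (120/25). The protocol's background section says the inflammatory reaction begins within a few hours of injury, so baseline POM is taken at different points of that process. Baseline POM may therefore not carry all the information in size and delay.

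Two things are at stake. First, whatever outcome variance these values explain beyond baseline POM, center and subgroup stays in the error term. That matters least for the overall test and most for tests 2a and 2b, which have fewer patients. Second, if the arms differ by chance in size or delay, no listed table would show it. An adjustment made after unblinding would then look driven by the data.

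**Working it through.** **1. Inputs from the documents** (protocol 9.9, SAP 6). Two-sided α of 5%. "Assuming SD = 20 mm, the sample size provides approximately 80% power to detect a difference of 10 mm" "if 64 patients per group are analysed". Then "the sample size will be stipulated to n=90 per group", and 200 in total after about 10% dropout.

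**2. Reproducing the plan's figures.** For the two-sample t-test, the noncentrality is 10 / (20·√(2/n)) on 2n − 2 degrees of freedom.
- n = 64: noncentrality 2.83, power 80.1%. This is the smallest n that reaches 80%.
- n = 90: noncentrality 3.35, power 91.6%.
- Dropout: 90 / 0.9 = 100 per arm, 200 in total.

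The stated sample size reproduces and relies on no covariate adjustment.

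**3. Subgroups.** The documents do not give the split. With an assumed even split, n = 45 per arm, noncentrality 2.37, power 65.0%.

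**4. Gain from the two covariates.** Their partial R², given baseline POM, center and subgroup, is not in the documents and is assumed to be 2 to 10%. Residual SD = 20·√(1 − R²), with two degrees of freedom removed:

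| Assumed partial R² | Residual SD (mm) | Power, 90 per arm | Power, 45 per arm |
|---|---|---|---|
| 0 | 20.0 | 91.6% | 65.0% |
| 0.02 | 19.8 | 92.1% | 65.9% |
| 0.05 | 19.5 | 92.8% | 67.2% |
| 0.10 | 19.0 | 94.0% | 69.6% |

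The 95% CI half-width at 90 per arm, 1.96·SD·√(2/90), falls from 5.84 mm to 5.70 mm at R² = 0.05 and to 5.54 mm at 0.10. The 10% case equals 90 / 0.9 = 100 per arm, or 10 extra patients per arm. Size alone, which is what the primary model would gain, delivers some part of this.

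**5. Sensitivity to what the 20 mm SD means.** The documents state it for a t-test. If it is the SD before adjustment, and baseline POM, center and subgroup already explain an assumed 25%, the starting SD is 20·√0.75 = 17.3 mm. At 90 per arm, power then moves from 97.1% to 97.3–98.2%, a smaller gain. At 45 per arm it moves from 77.3% to 78.1–81.4%, nearly the same gain as in the table.

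**6. Chance imbalance.** At 100 per arm the 95% range of a standardized mean difference is ±1.96·√(2/100) = ±0.28 SD. If size is uniform over 25 to 120 cm² (SD 95/√12 = 27.4), that is ±7.6 cm². If delay is uniform over 0 to 6 h (SD 6/√12 = 1.73), it is ±0.48 h. With an assumed correlation with outcome of 0.1, 0.2 or 0.3 and an SD of 20 mm, the estimate shifts by up to about 0.6, 1.1 or 1.7 mm.

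**7. Cost in precision.** If size explains nothing, spending one degree of freedom leaves power at 91.6% at 90 per arm and 65.0% at 45.

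**The case against.** The case against changing anything is substantial, and most of it stands as a limit on the claim.

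- **A reader might infer that the protocol calls delay a driver of success.** It does not. Section 2 says early treatment may help, which could describe a treatment effect that varies with delay as much as prognosis. A main-effect covariate does not address the former. The protocol's own response is to restrict entry to 6 hours, which is a legitimate design control. Nothing comparable is said about injury size.
- **A reader might infer that the primary test is biased or invalid.** It is not. Under 1:1 stratified randomization, omitting a baseline covariate causes neither bias nor type I error inflation, and the confidence interval already allows for chance imbalance. A shift of 0.6 to 1.7 mm is small beside a half-width of 5.84 mm and a 10 mm target.
- **A reader might infer that a loss of precision has been shown.** It has not. It depends on partial correlations the documents do not give, and the entry limits narrow the spread of both variables. The overall test already exceeds its 80% target.
- **Baseline tables may still show size.** Protocol 7.2 introduces its list as inclusive, and SAP 14.3 refers to other characteristics, so such a table is not excluded. It is simply not specified.
- **Delay may not be recorded.** The case report form is not among the documents. Injury time could be captured already or missing altogether, and a new Visit 1 field could come too late.
- **The model is fixed in the protocol too.** Changing only the SAP would set the two documents against each other.

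What these points leave intact is injury size. It is already measured on every patient, adjusting for it costs one degree of freedom, and the decision can be made blind. The objections to delay are why it belongs in a supportive analysis.

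**Conclusion.** The point holds as a low-cost improvement to a valid primary analysis. Injury size is available for every randomized patient, yet it is in neither the primary model nor the specified baseline list. Delay appears only as an entry limit, although the protocol says it may bear on treatment success.

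The overall test would gain about 0.5 to 2.4 percentage points of power (91.6% to 92.1–94.0%), and each subgroup test about 0.9 to 4.6 points (65.0% to 65.9–69.6%). These figures assume that the two covariates together explain 2 to 10% of residual variance, that 20 mm is the SD after the planned adjustment, and that the subgroups split evenly. If 20 mm is the unadjusted SD, the gain at 90 per arm is smaller. The reporting gap does not depend on these assumptions: no listed table would show an imbalance in either variable.

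**What to change.** Before unblinding:

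1. **Primary model.** In protocol 9.7.2 (with the synopsis) and SAP 14.4.1 together, add injury size in cm² as a continuous covariate to the primary ANCOVA and to tests 2a and 2b.
2. **Supportive model.** Pre-specify a supportive ANCOVA that also includes hours from injury to first patch, where the injury time can be obtained from the source used to check the 6-hour criterion. State how patients without a recorded time are handled, and define the interval explicitly, because the limit is tied to enrollment in one place and to treatment in others.
3. **Baseline tables.** Add both variables to SAP 5.3 and 14.3, summarised by arm and subgroup, with the number of missing injury times.

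The cost is one residual degree of freedom in the primary model and aligned wording in the two documents. The protocol part goes through the written amendment procedure of protocol 11.1. SAP section 1 says the SAP is finalized after the blind review meeting, so the change can still be made blind. A clock-time field at Visit 1 is needed only if the injury time is not already in the source records.
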